titration rates. The design provides robust statistical strength and controls for selection bias created by individual variability in cognitive performance. The use of healthy subjects will control for the effects of epilepsy, underlying brain dysfunction, and changes in seizure frequency on cognitive function. In addition, examining ASM cognitive effects in healthy subjects allows extrapolation of the results to other patient populations that might be potentially treated with ASMs (e.g., tremor, pain). We have conducted multiple studies with similar design with an excellent safety record that have provided clear delineation of the cognitive side effects of ASMs ([name], et al. 2019).

II. STUDY QUESTIONS

1. What are the behavioral, cognitive or other side effects of perampanel at different titration rates in healthy volunteers?
2. What is the time course of habituation to objective vs. subjective neuropsychological (e.g., cognitive and behavioral) side effects of perampanel?

III. STUDY OBJECTIVE

The objective of this study is to determine whether there are any differences in the cognitive abilities and/or behavioral response of normal healthy volunteers across different titration rates of perampanel.

IV. STUDY DESIGN

The study will employ a randomized, double-blind, parallel group design across different titration rates of perampanel in healthy volunteers. Every subject will be treated with perampanel (PER) at one of four different titration rates: (1) 2mg/day PER for one week followed by 4mg/day PER for five weeks, (2) 2mg/day PER for two weeks followed by 4mg/day PER for four weeks, (3) 4mg/day PER for six weeks, or (4) placebo (0mg/day PER) for six weeks. A study physician will monitor each subject during ASM treatment period. Subjects will undergo cognitive, behavioral, and safety testing at screening, prior to initiation of the first dose, and at the end of each week during the titration and maintenance period. Subjects and study personnel in direct contact with subjects will be blinded to ASM treatment.

V. STUDY POPULATION

A. Number and type of subjects

Healthy males and females between the ages of 18 and 55 who do not require concomitant medications that affect study medications or cognitive and behavioral functions. One hundred and three subjects across three academic medical centers (Stanford University, New York University, and Northwestern University) will be enrolled in the study in order to complete 76 subjects.

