PER ^b -3			4mg	4mg	4mg	4mg	4mg	4mg
Partial NP ^c			X	X		X	X	
Full NP ^d	X	X			X			X
TEAEs ^e	X	X	X	X	X	X	X	X

Testing is at the end of each week.

^aBL = baseline visit.

^bPER = perampanel.

^cPartial NP = partial neuropsychological battery on non-clinic visit weeks refers to online CNS-Vital Signs computerized cognitive tests and behavioral questionnaires (POMS-total, AEP, & QOLIE-89 cognitive scores, which will be mailed back).

^dFull NP = full neuropsychological battery includes Non-computerized cognitive tests and the Partial NP (questionnaires and online CNS-Vital Signs computer tests).

^eTEAEs = treatment emergent adverse events.

The investigative team will monitor each subject's progress and safety during ASM treatment periods. Subjects will remain in their treatment arm for a total of 6 weeks.

D. Enrollment Goals

Previous studies indicate that an enrollment of 103 subjects will be required to obtain 76 evaluable subjects. See Statistical Section for power analysis.

E. Visit-Specific Treatment and Evaluation Sequence

Subjects will be randomly assigned to one of four possible titration schedules. Each titration schedule lasts 6 weeks.

At all visits, subjects will be advised on drug compliance and avoidance of medications which may adversely effect the results of cognitive function testing. Adverse events will be documented on the appropriate case report form. Appointments will be made for follow up visits and care will be taken to schedule all cognitive and behavioral function testing for a given subject at the same time of the day. Dosing of the study medication should be at approximately the same time of day (e.g., before the participant goes to sleep). However, due to the long half-life of perampanel, this is not critical. The time of testing and time of last 2 doses will be recorded.

The timetable for the study is listed in Appendix A. This is a visit-by-visit description of the events scheduled for each visit.

Visit 1 Screening Visit (-1 weeks prior to randomization)

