Subjects will be screened to assure they meet all of the inclusion criteria and none of the exclusion criteria. All eligible subjects will be required to give informed consent. A complete history, full physical examination, full neurologic examination, vital signs, laboratory screening (including urine pregnancy test for women of childbearing potential), urine drug screen, IQ screen with Peabody Picture Vocabulary Test, full cognitive battery (see below), and lifetime assessment of suicidal ideation/behavior measured by the Columbia-Suicide Severity Rating Scale (C-SSRS) will be obtained.

Visit 2 Baseline/Randomization (Study week 0)

At this visit all subjects who had successfully completed all screening tests and had no significant abnormalities on baseline laboratory, physical exam, neurologic exam, or IQ testing will be randomized to study drug. At this visit, neuropsychological testing will be conducted before the first dose of study drug is administered. Subjects will be randomized and study drug will be dispensed.

Visit 3 Home testing (Study week 1)

At this visit, a partial neuropsychological assessment of cognitive function and behavioral testing will be performed. The assessments at this visit consist of online CNS-Vital Signs computerized cognitive tests and behavioral questionnaires (Profiles of Mood States

(POMS), Adverse Events Profile (AEP), & cognitive/behavioral subsets of QOLIE-89). Partial neuropsychological assessment will be conducted. Telephone contact will be made to check on adverse events and to encourage compliance.

Visit 4 Home testing (Study week 2)

At this visit, a partial neuropsychological assessment of cognitive function and behavioral testing will be performed. The assessments at this visit consist of online CNS-Vital Signs computerized cognitive tests and behavioral questionnaires (Profiles of Mood States (POMS), AEP, & cognitive/behavioral subsets of QOLIE-89). Partial neuropsychological assessment will be conducted. Telephone contact will be made to check on adverse events and to encourage compliance.

Visit 5 Clinic testing (Study week 3)

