Subjects will be instructed to limit alcohol consumption to no more than ½ ounce of absolute alcohol equivalents per day (approximately one 12 oz. beer, or 1 mixed drink) and no more than 3 ounces per week. Regular consumption of caffeine is allowed but will be limited to two cups on test days. Subjects will be instructed not to consume alcohol 12 hours prior to cognitive and behavioral testing, , or take any over-the-counter medications for at least 72 hours prior to cognitive and behavioral testing. All concomitant medications will be recorded on the case report forms. Any concomitant medications and other agents, which are known to affect perampanel or have significant effects on cognition may not be taken during this trial. A partial list of examples include: anticholinergics, anticoagulants, antidepressants, antiepileptics, antipsychotics, anxiolytics, central nervous system depressants, corticosteroids, doxycycline, erythromycin, H2 antagonists, lithium, methylphenidate, narcotics, quinidine, reserpine, theophylline, and centrally active antihistamines.

IX. CLINICAL AND LABORATORY MEASUREMENTS

A. Clinical Efficacy Measurements (Study weeks -1, 0, 1, 2, 3, 4, 5, & 6)

Neuropsychological testing will be completed at screening (visit 1; study week -1), baseline (visits 2; study week 0), and each week of the ASM treatment period (visits 3-8; study weeks 1-6). The neuropsychological test results from the first screening testing (i.e., visit 1 at -1 weeks) will not be included in the analyses. All subjects will have at least 7 hours of sleep on the evening before the day of cognitive testing. (Note. If the subject does not get the required hours of sleep or takes non-approved medication, caffeine, etc., cognitive and behavioral testing will be rescheduled).

For detailed information regarding all of the cognitive tests refer to Section VII.

B. Clinical Safety Measurements

1. Physical Examinations (Study weeks -1, 3, & 6)

A complete physical and neurological examination will be performed during pre-study screening (visit 1; study week -1) and at the completion of the study (visit 8; study week 6) or early study discontinuation. Brief physical and neurological examinations will be performed at visit 5 (study week 3).

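### The ±3-day window and an unlimited reschedule rule allow the week-1 test in PER-1 and the week-2 test in PER-2 to fall after the step to 4 mg, and the analysis has no rule for such tests

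*Combined protocol and SAP*

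**What the plan says.** Section IV defines PER-1 as "2mg/day PER for one week followed by 4mg/day PER for five weeks" and PER-2 as "2mg/day PER for two weeks followed by 4mg/day PER for four weeks". PER-3 and placebo have no step. The note under the section VI.C table says "Testing is at the end of each week", and Appendix A sets target days 7 and 14 for the first two on-treatment tests. Footnote c of Appendix A allows every visit to move by three days either way.

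Section IX.A adds a reason to postpone: "If the subject does not get the required hours of sleep or takes non-approved medication, caffeine, etc., cognitive and behavioral testing will be rescheduled". It gives no maximum delay and does not say whether the dose step waits. Section VIII.F tells subjects not to "take any over-the-counter medications for at least 72 hours prior to cognitive and behavioral testing".

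On dosing, section VI.E says "Dosing of the study medication should be at approximately the same time of day (e.g., before the participant goes to sleep" and calls the half-life long without giving a number. At Visit 2, "neuropsychological testing will be conducted before the first dose of study drug is administered". Appendix A marks dispensing at Visit 2 only. Visits 3 and 4 are home tests with a telephone contact. The time of testing and the times of the last two doses are recorded.

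Section X.B fits a 4 (titration rate) by 6 (weeks 1 to 6) ANCOVA adjusted for baseline, with time as nominal week and no analysis windows. The per-protocol conditions in section X.D cover medication regimen, concomitant and OTC products, sleep, alcohol and caffeine, but not visit timing.

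**The concern.** Weeks 1 and 2 are the only weeks in which the perampanel arms are scheduled to take different doses. If the step follows the calendar and the test can slip past it, some PER-1 scores labelled week 1, and some PER-2 scores labelled week 2, come from subjects already taking the same daily dose as PER-3.

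The problem is specific to those arms: a late test in PER-3 or placebo crosses no step. If 4 mg has the larger effect, late tests pull PER-1 at week 1 and PER-2 at week 2 toward PER-3, which favours a finding of no difference between titration rates. Comparisons of the same two cells with placebo would shift the other way. The habituation curves for study question 2 would also carry a small timing error at those weeks.

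**Working it through.** The plan gives no figure for this point to reproduce. The sample-size figure in section X.A does not enter the check.

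**1. Doses of 4 mg before the test**

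Inputs: the step follows seven (PER-1) or fourteen (PER-2) daily doses; target day T = 7 or 14; window T-3 to T+3, that is days 4–10 and 11–17. The calendar step is inferred from the schedule and the single dispensing. The exact day and hour of the first dose are not stated, so three cases are shown.

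With a first dose on the evening of day 0, nights 0 to 6 are the seven 2 mg doses of PER-1 and night 7 is the first 4 mg dose. A daytime test on day 10 follows nights 7, 8 and 9, so three 4 mg doses. The counts are the same for PER-2 around day 14.

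| Dosing assumption | on target | +1 | +2 | +3 |
|---|---|---|---|---|
| Bedtime, first dose day 0 | 0 | 1 | 2 | 3 |
| Bedtime, first dose day 1 | 0 | 0 | 1 | 2 |
| Morning from day 0, before the test | 1 | 2 | 3 | 4 |

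Tests one to three days early follow none. The three-day bound comes from the Appendix A window. The reschedule rule is one route to a late test: an OTC product taken on day 7 moves a compliant test to 7 + 3 = day 10. If that rule is not bound by the window, the count could be higher.

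**2. Which cells are exposed**

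There are 4 × 6 = 24 arm-week cells, and two can cross a step inside the window: PER-1 at week 1 and PER-2 at week 2. PER-2 is on 2 mg through its whole week-1 window (to day 10, step after day 14), so PER-2 versus PER-3 at week 1 is clean. The week-3 window opens on day 21 - 3 = 18, after both steps.

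**3. Possible size for one subject tested at +3 days (illustration only)**

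Assumption: linear once-daily accumulation, half-life h between 24 and 120 hours. Let r = 0.5^(24/h), so r = 0.50 to 0.87. The level relative to PER-3 on the same day, d days after target, is 0.5 + 0.5 × (1 - r^d)/(1 - r^(T+d)).

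- PER-1, day 7 (d = 0): 50%.
- PER-1, day 10 (d = 3): 94% at 24 h, 73% at 120 h. The share of the relative contrast left is (1 - ratio)/0.5, so 12% to 55%.
- PER-2, day 17 (d = 3): 94% to 69%, leaving 12% to 62%.

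**4. Possible size for an arm mean (illustration only)**

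If a share f of the arm is tested late and each loses a share L of the contrast, the mean contrast kept is 1 - f × L.

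- f = 0.10, L = 0.50: 95% kept. A comparison with 80% power (two-sided 0.05 assumed) would have about 76%.
- f = 0.25, L = 0.50: 87.5% kept; about 69%.

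Power here is Φ((1.96 + 0.84) × kept - 1.96). Neither f nor L can be taken from the documents.

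**The case against.** The strongest reply is that the effect is local. The primary model uses six weeks and four arms. Section X.A places the maximum effect of the slower PER-2 arm at the end of week 3, and the first secondary outcome compares weeks 3 and 6. All of that is clear of the step. The analysis is also by assigned titration rate, not by current dose, so a late score is not formally mislabelled as a 2 mg score. Both points stand and limit the size. They do not explain why a test meant for the end of a dose period may fall in the next one.

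Recall periods soften the effect on questionnaires. POMS asks about the past week, and QOLIE-89 does so where appropriate. With a seven-day recall on day 10, 7 - 3 = 4 of the days are still 2 mg days. This reduces the dilution of the subjective part but does not remove it.

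Recorded test and dose times let a late test be identified. However, two dose times cannot date a step that was three doses earlier, and no analysis uses them.

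Moving tests earlier has its own cost. In the same model, the PER-3 minus PER-1 level difference on day n ≤ 7 is proportional to 1 - r^n. A day-4 test would therefore lose about 6% (24 h) to 31% (120 h) against day 7, while a day-10 test loses 1 - r^3, or 87% to 34%. With a long half-life, a wide early window gives up almost what it saves. At one day early the loss is 1 - (1 - r^6)/(1 - r^7), about 1% to 9%. So only a short early allowance is justified.

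A reader might infer that symptomatic subjects are the ones tested late, since section IX.C lists headache and an OTC remedy triggers the 72-hour rule. The documents do not support this as a finding. The same list has sleepiness and tiredness, which could make seven hours of sleep easier, and no reschedule rate by arm or symptom is given. It is a possible risk only.

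**Conclusion.** The concern holds in a limited form. As written, the plan permits the week-1 test in PER-1 and the week-2 test in PER-2 after up to three 4 mg doses (bedtime dosing from day 0; 2 to 4 across the dosing cases), and it has no rule for such tests. This can dilute PER-1 versus PER-3 at week 1 and PER-2 versus PER-3 at week 2. It rests on one inference, that the step follows the calendar week and does not wait for the test.

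The size is unknown; the accumulation and power figures show only what could happen under stated assumptions. Two further readings go too far. The titration comparison as a whole is not compromised, because 22 of the 24 cells are untouched. Nor can the dilution be judged against 0.24/3 = 0.08 z between adjacent arms: section X.A assumes equal spacing at the time of maximum effect, which it sets at week 1 for PER-3 and week 3 for PER-2, so 0.08 is not a same-week contrast at week 1 or 2.

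**What to change.** In Appendix A, for events 3 and 4 in all four arms (to keep the blind), require the test by the target day (7 or 14) and before any possible step, with a short early allowance, for example -1/0 days. Keep ±3 days elsewhere. With bedtime dosing this brings the 4 mg doses before an on-time test to 0 (0 to 1 with morning dosing).

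Keep the sleep, caffeine and OTC conditions. Testing despite a failed condition would set aside a safeguard of section IX.A and cost the subject per-protocol status under section X.D. Some tests will therefore still slip past the target day. For these, section X.B should:

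- keep the score in the primary analysis by randomised arm and nominal week;
- use the actual date of the step, collected in the same way in all arms;
- prespecify a sensitivity analysis that excludes or reclassifies event 3 and 4 tests done after the step.

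Section IX.A should state a maximum delay. If the step is meant to wait for the test, sections IV, VI.C and IX.A and Appendix A must be reconciled to say so. No change to the dosing schedule is proposed.

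The cost is amendment wording, one added data item, and tighter scheduling of two online home tests.

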B. Inclusion Criteria

1. Healthy adults between the ages of 18 and 55 years
2. Male or female (using approved birth control methods)
3. Informed consent obtained

C. Exclusion Criteria

1. Presence of clinically significant cardiovascular, endocrine, hematopoietic, hepatic, neurologic, psychiatric, or renal disease.
2. Presence or history of drug or alcohol abuse or positive urine drug test at screening.
3. The use of concomitant medications, which are known to affect perampanel or the use of any concomitant medications that may alter cognitive function (see Section VIII.F for a partial list).
4. Prior adverse reaction to or prior hypersensitivity to perampanel.
5. Prior participation in studies involving perampanel.
6. Subjects who have received any investigational drug within the previous thirty days.
7. Subjects with IQ \leq 80 as determined by the Peabody Picture Vocabulary Test after enrollment.
8. Positive pregnancy test. Women of childbearing potential will be required to use approved birth control methods during the study.
9. Presence of lifetime history of suicide attempt (including an active attempt, interrupted attempt, or aborted attempt), or has suicidal ideation in the past 6 months as indicated by a positive response ('Yes') to either Question 4 or Question 5 of the C-SSRS at Screening.
10. Invalid results on computerized cognitive tests at screening as indicated by a 'No' on any of the validity indicators generated in the CNS Vital Signs report and low effort on neuropsychological assessments per investigator judgement.

VI. STUDY PROCEDURES

A. Overview: time and events

The study will employ a randomized, double-blind, parallel group design across different titration rates of perampanel in healthy volunteers. The study consists of 8 visits over an 8-week time period. Subjects will be screened and tested at baseline, and then randomly assigned to receive one of four titration schedules, each lasting 6 weeks. (See Appendix A for a complete study timetable).

B. Blinding and Controls

Subjects and study personnel will be blinded to drug randomization since all study drugs will be over-encapsulated in identical capsules.

C. Dosage Regimen

Subjects will be titrated up to 4mg/day PER or receive placebo according to the dosage schedule below:

Event	1	2	3	4	5	6	7	8
Week	Screen	BL ^a	1	2	3	4	5	6
Clinic Visit	X	X			X			X
Placebo			0mg	0mg	0mg	0mg	0mg	0mg
PER ^b -1			2mg	4mg	4mg	4mg	4mg	4mg
PER ^b -2			2mg	2mg	4mg	4mg	4mg	4mg

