Provisions for prorating payment: If perampanel levels tested at visits 5 and 8 are below detectable levels, this indicates that the participant was not complying with the protocol and they will not receive their final payment of \$400 for visit 8. Please note that this only applies to participants assigned to the three perampanel groups, not the placebo group.

VII. NEUROPSYCHOLOGICAL TESTS

A. Outline:

Note that test will be performed in the following order.

Computerized Testing Battery (CNS Vital Signs system)

- Verbal memory immediate assessment
- Visual memory immediate assessment
- Symbol digit coding assessment
- Shifting attention test
- Dual task test
- One- and two-back continuous performance test
- Verbal memory delay assessment
- Visual memory delay assessment

Non-computerized cognitive/behavioral testing

- MCG paragraph memory-immediate recall assessment
- Symbol digit modalities test
- Stroop test
- Profile of mood states (POMS) assessment
- AEP
- QOLIE-89 cognitive domains (attention/concentration, language, memory)
- MCG paragraph memory-delay recall assessment
- Columbia-Suicide Severity Rating Scale

B. Description of Individual Tests:

1. Components for computerized cognitive assessments:

The computerized cognitive assessments have been used in prior studies (see reference section for CNS Vital Signs). It consists of verbal memory immediate assessments, visual memory immediate assessments, symbol digit coding, shifting attention tasks, dual task tests, one- and two-back continuous performance tests, verbal memory delayed, and visual memory delayed. Detailed descriptions of each are below.

1a. The order of computerized testing should be as follows:

- Verbal memory immediate
 - Encoding - 30 seconds
 - Immediate recognition - 1 minute
- Visual memory immediate
 - Encoding - 30 seconds
 - Immediate recognition-1 minute
- Symbol digit coding - 2 minutes
- Shifting attention test - 2 minutes
- Dual task test - 2 minutes
- One- and two-back continuous performance test - 5 minutes
- Verbal memory delayed - 1 minute
- Visual memory delayed - 1 minute

These are actual test run times and do not include reading instructions or practice tests.

1b. Verbal memory immediate assessment:

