A complete physical examination will consist of determinations of sitting blood pressure, weight, heart rate, assessment of physical condition (general appearance, skin and skin structure, HEENT, abdomen, cardiovascular, respiratory, musculoskeletal, genitourinary and central nervous systems). Brief physical examinations will consist of determinations of sitting blood pressure, weight, heart rate, and an assessment of physical condition, as required to determine change from the previous visit, and an assessment of adverse effects focused on skin and neurological systems.

2. Laboratory assessments (Study weeks -1 and 6)

A. Blood and Urine Samples

Blood work assessments will be obtained at visits 1 & 8.

The hematology parameters to be determined are: RBC count, hemoglobin, hematocrit, WBC count, platelet count, cell morphology and complete WBC differential count (neutrophils, bands, lymphocytes, monocytes, eosinophils and basophils).

The chemistry parameters to be determined are: SGOT, SGPT, alkaline phosphatase, albumin, total protein, total bilirubin, sodium, potassium, chloride, calcium, phosphorous, creatinine, blood urea nitrogen, uric acid and glucose. The total chemistry panel will be obtained at visits 1 & 8.

Urine Pregnancy tests will be performed on women of childbearing potential at study weeks -1, and 6 (visits 1 & 8).

Blinded PER blood levels will be collected at study weeks 3 and 6 (i.e., visits 5 & 8). PER levels will be sent to an outside contract lab. PER levels may be sent to the hospital laboratory for immediate analysis if testing is available. Results are to be reviewed and stored by a non-blinded investigator.

C. Adverse Event Procedures

An ADVERSE EVENT (AE) is a noxious and unintended event observed in, or reported by, a subject who is participating in (or has participated in) a clinical study and/or has received study medication. The AE may be related temporarily either to immediate or long-term use of the drug; the AE may not necessarily be caused by the drug. Overdose is regarded as an adverse event. Any event meeting these criteria is to be considered an adverse event, regardless of whether or not it is considered drug related.

All adverse events will be reported on the appropriate Case Report Form; details should include the type of event, date of onset, duration, intensity, causality relationship to the study drug(s), and outcome. Wherever possible, a diagnosis rather than symptom(s) should be reported.

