 - d. Consent is withdrawn. Subjects will be encouraged to complete the study, although they may withdraw at any time without prejudice.
4. Subject replacement.

Subjects who are dropped from the study prior to completion of all cognitive testing will not be replaced.

Subjects who are withdrawn prior to completion of at least one set of cognitive testing on treatment drug (i.e., prior to visit 5/study week 3) may be replaced.

5. Follow-up of discontinued patients

Subjects who receive study drug and are discontinued from the study will have all safety assessments completed, including a complete physical examination and laboratory evaluation including chemistry, hematology with differential, urinalysis and urine pregnancy test as required at study termination. This testing should be done as soon as possible. Medical follow-up of any severe adverse events or clinically significant abnormal laboratory values will continue until the abnormality resolves, and adequate medical explanation is apparent. Such data will be provided to Eisai.

X. STATISTICAL EVALUATION

A. Sample Size

We assume that the 4 groups (3 PER treatments and a placebo group) are equally spaced (in terms of z-score) at the time point of maximum drug effects (end week 1 for 4mg group and end week 3 for titration to 2mg x2wks then 4mg group), with a maximum difference of 0.24 (which is the difference between the placebo group and treatment at max effect). We then assume that over the 4 visits after max drug effect the z-scores get closer together until

they are equal at the treatment week 6th. The calculation indicates that at least 18 subjects are needed in each group to have 80% power. Since there are 4 groups, the total sample at least finishing assessment at end of week 6 (event 8) would be $19 \times 4 = 76$. Enrollment will include 20% (n=15) more to account for dropouts prior to assessment at end of visit 2 (baseline), and ~15% (n=12) more for dropouts before end of event 8 (treatment week 6). Thus, the total enrollment sample will be 103 subjects.

In summary, the 4 total groups (3 PER treatment, 1 placebo) would need at least 19 subjects per group (76 total), and total enrollment would be rounded to 105 to account for dropouts.

B. Methodology for statistical analysis

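### No pregnancy test is scheduled at Visit 2, where drug is dispensed, so the only pre-dose result is 7 to 21 days old

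*Combined protocol and SAP*

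**What the plan says.** Three places in the protocol set the pregnancy test schedule, and they agree.

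- IX.B.2: "Urine Pregnancy tests will be performed on women of childbearing potential at study weeks -1, and 6 (visits 1 & 8".
- VI.E includes the test in the laboratory work at Visit 1 and Visit 8 and in no other visit description.
- Appendix A marks it at events 1 and 8 and leaves event 2 blank.

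Visit 2 is where treatment starts. VI.E says "Subjects will be randomized and study drug will be dispensed", and Appendix A has its only dispensing mark there. The subjects taken forward are those with "no significant abnormalities on baseline laboratory, physical exam, neurologic exam, or IQ testing will be randomized to study drug". Blood work is drawn only at Visits 1 and 8 (IX.B.2), so the laboratory results relied on at Visit 2 are those from screening. Footnote a of Appendix A allows screening to be one to three weeks ahead of baseline; VI.E gives one week as the nominal interval.

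The relevant exclusion, V.C item 8, reads "Positive pregnancy test. Women of childbearing potential will be required to use approved birth control methods during the study". Inclusion criterion 2 (V.B) also makes approved birth control a condition of entry. For subjects discontinued after receiving drug, IX.E item 5 calls for "urinalysis and urine pregnancy test as required at study termination".

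**The concern.** A woman can test negative at screening, conceive before Visit 2, and be randomized and given drug with the protocol followed to the letter. Nothing scheduled at Visit 2 would reveal the pregnancy. Three of the four arms are active, so under equal allocation she has a 3 in 4 chance of receiving perampanel. Weeks 1 and 2 are home visits. The first clinic visit on drug, at week 3, has no pregnancy test, and the next scheduled one comes when dosing is over.

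These are healthy volunteers, with no therapeutic benefit to set against the exposure. What is at stake is subject safety; the primary analysis, the power and the type I error are not affected.

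**Working it through.** This is calendar arithmetic on the schedule.

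**Inputs**
- Screening to baseline: 1 to 3 weeks (Appendix A, footnote a); nominally day -7.
- Randomization and dispensing: day 0 (VI.E Visit 2; Appendix A).
- Next scheduled pregnancy test: Visit 8, day 42, with a window of 3 days either side (Appendix A, footnote c), so days 39 to 45.
- Visit 5, a clinic visit: day 21.
- Arms: three perampanel, one placebo; X.A plans 19 per group.

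**Schedule as written**
1. Age of the pregnancy result at dispensing: 1 × 7 = 7 days to 3 × 7 = 21 days. If the 3-day window also applies to this interval, which the documents leave unclear, the range is 7 − 3 = 4 to 21 + 3 = 24 days.
2. Dispensing to next scheduled test: 42 − 0 = 42 days (39 to 45 with the window).
3. First to second scheduled test: 7 + 42 = 49 to 21 + 42 = 63 days. With the Visit 8 window: 7 + 39 = 46 to 21 + 45 = 66 days.
4. Chance of an active arm under equal allocation: 3/4 = 75%.

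**What the existing safeguards check before the first dose**
- Contraception (inclusion 2, exclusion 8) lowers the chance of conception but does not verify status. The protocol tests these women at screening despite the requirement, so it does not treat contraception alone as sufficient.
- Adverse events are reviewed at every visit, which is not a test.
- The early-discontinuation test comes after exposure.

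**With a test at Visit 2**
1. Age of the result at first dose: 0 days instead of 7 to 21.
2. Longest scheduled gap between tests: 42 days (39 to 45) instead of 49 to 63.
3. Share of the original gap that remains: 42/63 = 67% to 42/49 = 86%. The test removes the part before dosing and leaves the part on drug.
4. With a further dipstick at Visit 5: 21 − 0 = 21 days, then 42 − 21 = 21 days.

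**The case against.** The strongest reply is that this is a deliberate and consistent schedule. The visit text, the laboratory section and the timetable agree, and nothing in the protocol requires a test on the day of first dose. That is right, and the point is put here as a safety gap only.

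A second reply concerns exclusion 8. A reader might infer that, because it names no visit while item 2 specifies "positive urine drug test at screening", the protocol breaches its own criterion at Visit 2. The documents do not support that. VI.E has Visit 1 apply all the entry criteria, the pregnancy test is part of that visit, and several other exclusions also name no visit. The screening test does apply exclusion 8; what remains is its age.

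Third, contraception is an entry condition as well as a rule during the study, so the interval before dosing is covered by a requirement. This stands as mitigation and is a reason to expect few cases. It does not confirm status before dosing.

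Fourth, a Visit 2 test does not shorten the six weeks on drug. This also stands. The figure that supports the Visit 2 test is the 7 to 21 days; the 42 days would support a separate test at Visit 5. Nor can a Visit 2 test be relied on to detect a conception only days old.

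**Conclusion.** The point holds as a cheap safety improvement. The sole pre-dose pregnancy result is 7 to 21 days old when drug is dispensed (nominally 7), and no other provision checks status before the first dose. The size rests on footnote a being used as written. The documents give no conception rate, so no expected number of cases is offered. The 75% chance of active drug assumes equal allocation.

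A reader might also infer that VII.A and Appendix A conflict over a suicidality assessment at Visit 2, because VII.A ends its list of non-computerized testing with the "Columbia-Suicide Severity Rating Scale" and the full battery is given at Visit 2. The documents do not support that reading. VII.A sets the order of testing and names no visits. VI.E and Appendix A both assign the scale to Visits 1, 5 and 8 and keep it apart from the battery, and neither definition of the full battery names it. Exclusion 9 is tied to answers given "to either Question 4 or Question 5 of the C-SSRS at Screening", which the Visit 1 assessment satisfies. No defect is claimed there.

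**What to change.** In Appendix A (event 2), VI.E Visit 2 and IX.B.2, add a urine pregnancy test for women of childbearing potential at Visit 2, to be read before randomization and dispensing. Reword the opening of exclusion 8 to: *Positive pregnancy test at Screening or Visit 2*.

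Optionally, add a dipstick at Visit 5, already a clinic visit, if the sponsor also wants to shorten the interval on drug to about 21 days.

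Cost: an amendment and no new visits. X.A allows for 15 of the 103 enrolled dropping out before the end of Visit 2, so 103 − 15 = 88 to 103 subjects reach it. The share who are women of childbearing potential is not given; assuming 30% to 60%, the Visit 2 test needs 0.30 × 88 = 26 to 0.60 × 103 = 62 dipsticks. Footnote m of Appendix A plans Visit 2 without a clinic room or physician unless one is needed, so sites must arrange urine collection, someone to read the result before dispensing, and follow-up of any positive. A few subjects may be excluded after their screening costs have been spent. The sample size calculation and the analysis plan need no change.
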